3. RISK/BENEFIT ANALYSIS

3.1. Potential Risk to the Subject

The KODEX-EPD system used in this study is cleared for commercial use by the FDA and is CE-certified; therefore, the use described in this protocol constitutes a standard clinical use. Information related to contraindications, adverse effects, warnings and precautions are included in the device instructions for use. Patients enrolled do not bear additional clinical risk by participating in this study.

The sponsor has taken all the necessary precautions and applied the required mitigations, as described in the risk analysis document, in order to make even the rarest risk become virtually impossible.

Nevertheless, potential complications that could be related to the system include, but are not limited, to the following anticipated AEs:

- Skin allergy due to body external patches
- Secondary transient hyper-hydrosis due to local skin irritation
- Local superficial burns (return electrode)
- Hampering the quality of recorded intra-cardiac electrical signals that are being transferred to the recording system through the KODEX-EPD system (noise introduction)
- Decreasing the power output of the RF generator; thereby potentially affecting the generated ablation lesions
- Incorrect reading of the catheter's tip electrode impedance at rest or during ablation as presented on the RF generator front panel
- Incorrect reading and presentation of the tip electrode temperature as read by the RF generator
- Incidental electrocution

3.2. Potential Benefits to the Subject

No direct benefits to the patient are expected.

3.3. Benefit-Risk Rationale

The KODEX-EPD and accessories used for the PROOF Study will be commercially available and are considered to be SOC for subjects indicated for cryoballoon PVI Procedures. The risks involved with subject participation in this study are essentially the same as those for subjects not participating in the study.

4. SAFETY DATA COLLECTION, RECORDING AND REPORTING

Adverse events and serious adverse events as defined below will be captured once the patient has signed the informed consent form. However, the primary endpoint analysis will count only adverse events for patients that the KODEX-EPD system has been used during the treatment procedure.

4.1. Definitions

4.1.1. Adverse Events (AE)

Any untoward medical occurrence, unintended disease or injury, or untoward clinical signs (including abnormal laboratory findings) in subjects, users or other persons, whether or not related to the KODEX-EPD system or accessories and whether anticipated or unanticipated. This definition includes events related to the investigational medical device or the comparator.

Additionally, this definition includes events related to the procedures involved.

For users or other persons, this definition is restricted to events related to the use of the KODEX-EPD system or accessories or comparators.

This definition includes events related to the procedures involved.

4.1.1. Adverse Device Effect (ADE)

An adverse event related to the use of KODEX-EPD System or accessories or the comparator.

This definition includes adverse events resulting from insufficient or inadequate instructions for use, deployment, implantation, installation, or operation, or any malfunction of the KODEX-EPD System. This definition includes any event resulting from use error or from intentional misuse of the KODEX-EPD System.

4.1.2. Serious Adverse Event (SAE)

The Investigator must decide whether each event meets the definition of a “serious” adverse event (SAE). SAE is defined as any adverse event that:

- Led to death,
- Led to a serious deterioration in health of the subject, users or other persons that either:
 - Resulted in a life-threatening illness or injury, or
 - Resulted in a permanent impairment of a body structure or a body function including chronic diseases, or
 - Required in-patient hospitalization or prolongation of existing hospitalization, or
 - Resulted in medical or surgical intervention to prevent life-threatening illness or injury or permanent impairment to a body structure or a body function.
- Led to fetal distress, fetal death, a congenital abnormality, or birth defect including physical or mental impairment

NOTE: A planned hospitalization for pre-existing condition, or a procedure required by the Clinical Investigation Plan, without a serious deterioration in health, is not considered to be a SAE.

4.1.3. Serious Adverse Device Effect (SADE)

An adverse device effect (section 4.1.1) that has resulted in any of the consequences characteristic of a serious adverse event as mentioned in section 4.1.2.

4.1.4. Unanticipated Serious Adverse Device Event (USADE)

An unanticipated serious adverse device event (USADE) is defined as any serious adverse device effect which by its nature, incidence, severity or outcome has not been identified in the current version of the risk analysis report.

NOTE: Anticipated: an effect which by its nature, incidence, severity or outcome has been previously identified in the risk analysis report.

4.1.5. Device Deficiencies

A device deficiency is an inadequacy of a medical device related to its identity, quality, durability, reliability, usability, safety, or performance, such as malfunction, misuse or use error and inadequate labeling. This definition includes device deficiencies related to the KODEX-EPD System or accessories or the comparator.

All KODEX-EPD system device deficiencies will be documented in the CRF. Devices that malfunction during the procedure will be analyzed by the sponsor, after appropriate decontamination per hospital guidelines.

Device deficiencies are NOT to be reported as AEs. However, if there is an AE that results from a device deficiency, that specific event would be recorded on the appropriate CRF.

4.1.5.1. Malfunction

A malfunction is a failure of the KODEX-EPD System or accessories or the comparator to perform in accordance with its intended purpose when used in accordance with the instructions for use or CIP, or IB.

4.1.5.2. Use Error

A use error can be defined as a user action or lack of user action while using the KODEX-EPD System or comparator that leads to a different result than that intended by the manufacturer or expected by the user. This includes the ability by the user to complete a task.

NOTE: A malfunction of a medical device that causes an unexpected result is not considered a use error, nor does an unexpected physiological response of the patient.

4.2. Adverse Event Classification

4.2.1. Severity Classification

Severity will be defined according to the following criteria:

Mild	Awareness of event, but easily tolerated
Moderate	Discomfort enough to cause some interference with activities of daily living (ADL)
Severe	Incapacitating, with an inability to perform ADL

4.2.2. *Relationship Classification*

The investigator's assessment of an AE/SAE's relationship to study device is part of the documentation process, but it is not a factor in determining what is or is not reported in the study. If there is any doubt as to whether a clinical observation is an AE/SAE, the event should be reported. The relationship or association of the study device in causing or contributing to the AE/SAE will be characterized as one of the following:

- **Not Related:** No relationship between the AE and the administration of study treatment and a known relationship to other etiologies such as concomitant medications, or subject's clinical state.
- **Possibly Related:** An AE that follows a reasonable temporal sequence from the use of the study device/procedure and follows a known response pattern to the study device/procedure but could have been produced by the participant's clinical state or by other therapies.
- **Probably related:** An AE that follows a reasonable temporal sequence from the use of the study device/procedure; follows a known response pattern to the study device/procedure; and cannot be reasonably explained by the known characteristics of the participant's clinical state or by other therapies.
- **Related:** An AE that follows a plausible temporal sequence from the use of the study device/procedure; follows a known response pattern to the study device/procedure. The reaction cannot be reasonably explained by the known characteristics of the subject's clinical state or other modes of therapy administered to the subject.
- **Unknown:** Given the information available, sequence and timing of events, it is unknown or impossible to determine the relationship between the AE and the study device/procedure.

4.2.3. *Outcome Classification*

Outcome of the event will be defined according to the following:

- **Resolved:** The event has fully resolved at the end of the study.
- **Resolved with sequelae:** The event has resolved, but retained pathological conditions resulting from the prior disease or injury.
- **Continuing:** The event is ongoing at the end of the study.
- **Death:** This event is determined to be the cause of death.

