4.3. Reporting

4.3.1. *Reporting of AEs and ADEs*

Information about all adverse events, whether volunteered by the patient, discovered by investigator questioning, or detected through physical examination, laboratory test or other means, will be collected and recorded on the Adverse Event e-CRF and followed as appropriate.

For the purpose of this study we will selectively collect AEs; meaning that only AEs directly or indirectly related to the EP intervention and/or any cardiac arrhythmia will be collected. Selective AE reporting is in line with the FDA's approach to a safety assessment that is focused on information that is useful and adds to current knowledge.

As far as possible, each adverse event will also be described by:

- its duration (start and end dates)
- the severity
- its relationship to the study device (unrelated/possible/probable)
- the action(s) taken

4.3.2. *Reporting of SAEs SADEs and USADEs*

For the purpose of this study and based on the definitions above and the requirements of the European authorities the following events are considered reportable events in accordance with Annex 7, section 2.3.5 and 93/42/EEC respectively:

- Any SAE whether or not considered as related to study device
- Any KODEX-EPD system deficiency that might have led to a SAE if:
 - a. Suitable action had not been taken, or
 - b. Intervention had not been made, or
 - c. If circumstances had been less fortunate
- New findings /updates in relation to already reported events

All USADEs, SAEs and SADEs, will be reported on specific forms, if applicable, and forwarded to the Sponsor within 24 hours of first awareness of the event. The Investigator is also responsible for complying with the applicable local requirements related to adverse event reporting.

The investigator must complete the appropriate event report form in English, assess the relationship to study device/procedure and e-mail the completed form to the Sponsor at:

[contact].

Follow-up information about previously reported USADEs, SAEs and SADEs must also be reported to the Sponsor within 24-hours of receipt. The Follow up information should be reported on a new event report form by referring to the subject and event number. Only new/updated information needs to be entered on the event report form.

Original and the duplicate copies of the event report forms must be kept at the study site. The monitor will review and collect copies of the completed event report forms and related documentation.

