If the SAE has not been previously documented (new occurrence) and it is thought to be related to study device, Sponsor's Medical Expert may contact the investigator to obtain further information. If warranted, an investigator alert may be issued, to inform all investigators involved in any study with the same device that this serious adverse event has been reported.

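### Every category in 4.2.2 that asserts a device relationship requires a known response pattern, so read literally some serious effects of a new kind cannot be labelled ADE, SADE or USADE; 4.3.1 also uses a different, shorter scale.

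*Combined protocol and SAP*

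**What the plan says.** Section 4.2.2 (Relationship Classification) asks the investigator to place each AE or SAE in one of five categories. Three of them assert a relationship:

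- Possibly Related: the event "follows a known response pattern to the study device/procedure but could have been produced by" the patient's condition or other treatment.
- Probably related: it "follows a known response pattern to the study device/procedure; and cannot be reasonably explained by" those alternatives.
- Related: it "follows a known response pattern to the study device/procedure. The reaction cannot be reasonably explained" by them.

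Not Related requires "No relationship between the AE and the administration of study treatment and a known relationship to other etiologies". Unknown is for events whose relationship cannot be determined.

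The device-effect labels build on each other. An ADE (the second section numbered 4.1.1) is "An adverse event related to the use of KODEX-EPD System or accessories or the comparator". A SADE (4.1.3) is an ADE with serious consequences. A USADE (4.1.4) is a SADE "which by its nature, incidence, severity or outcome has not been identified in the current version of the risk analysis report".

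Section 4.3.1 asks for each adverse event to be described by, among other things, "its relationship to the study device (unrelated/possible/probable"), which is three levels. Section 4.3.2 provides for sponsor follow-up, and an investigator alert if warranted, on this condition: "If the SAE has not been previously documented (new occurrence) and it is thought to be related to study device".

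**The concern.** The USADE label exists to pick out serious device effects that nobody foresaw. One way of being unforeseen, named in 4.1.4, is to be new in nature. A response pattern that is already known is close to the opposite of that, yet 4.2.2 makes it a condition of every rating that asserts a relationship. A site that applies the scale as written could withhold the rating that the USADE label needs, for the events the label was written for.

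At stake are the ADE, SADE and USADE labels, the counts built from them, and the alert step in 4.3.2. The mismatch between 4.2.2 and 4.3.1 adds a practical difficulty: an event rated Unknown under the first section has no level to go to under the second. Sites that resolve these gaps by judgement may resolve them differently.

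**Working it through.** No arithmetic beyond counting applies. The check traces one test event through the definitions.

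**Test event.** A serious event of a new kind. It fits the timing of device use and matches no known device or procedure pattern. The device worked and was used as intended, with adequate instructions. No other cause is known.

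**Step 1: rating under 4.2.2.**

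| Category | Condition that decides | Open to the test event? |
|---|---|---|
| Not Related | No relationship, plus a known other cause | No |
| Possibly Related | Known response pattern | No |
| Probably related | Known response pattern | No |
| Related | Known response pattern | No |
| Unknown | Relationship cannot be determined | Yes, by default |

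In all three middle rows the pattern condition is added to the timing condition; it is not an alternative to it. So 3 of the 3 categories asserting a relationship carry the condition, and 0 of 3 are open to the test event.

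**Step 2: labels under 4.1.** Unknown does not assert a relationship. The event therefore does not meet the ADE definition through relatedness. Without ADE there is no SADE, and without SADE there is no USADE.

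**Step 3: which events escape the problem.**

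- The ADE definition directly includes events resulting from malfunction, use error, intentional misuse or inadequate instructions. These are ADEs whatever their 4.2.2 rating.
- The pattern in 4.2.2 may be a device pattern or a procedure pattern, while USADE status is judged against the risk analysis report. An event that follows a known procedure pattern but is absent from that report can be rated related and be a USADE.
- An effect of a known kind can still be a USADE through unexpected incidence, severity or outcome.

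What remains is the test event as specified.

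**Step 4: comparison with 4.3.2.** That section expects that an SAE can be both a new occurrence and thought to be device-related. For the test event, 4.2.2 read literally does not allow the second half. The two sections do not fit together.

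**Step 5: comparison of the scales.** Section 4.2.2 has five levels and 4.3.1 has three. The three correspond to Not Related, Possibly Related and Probably related, so 5 − 3 = 2 levels, Related and Unknown, have no counterpart in 4.3.1.

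**Step 6: what depends on the rating.** The labels and their counts do, and in practice the alert step may. SAE reporting does not: 4.3.2 makes every SAE reportable whatever its relationship and sends it to the sponsor within 24 hours, and 6.1 has the investigator notify the IRB/EC of SAEs alongside USADEs under local procedures.

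**The case against.** The strongest reply is that nothing serious goes unseen. Section 4.2.2 itself says the relationship rating does not determine what is reported. The sponsor and IRB/EC routes for SAEs do not depend on it. Section 8.3 separately has the sponsor and investigator discuss any sign of unknown or increased risk. Follow-up is not shortened either: the 30-day limit in 2.6.5 and 8.3.2 covers AEs and SAEs that are not study-related, and an SAE rated Unknown has not been rated unrelated. All of this stands, and it confines the point to classification.

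A second reply is that the ADE definition never cites the 4.2.2 scale, and that the alert step turns on what is thought to be related, without naming a rating level or whose view counts. Both are true. But 4.2.2 is the only place where relationship categories are defined, and a site has no other written standard to use. The alert step is discretionary, so any loss there is possible, not certain.

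A third reply is that the list in 4.3.1 only describes AEs as far as possible, and that serious events fall under 4.3.2, which does not repeat the three levels. That makes the scale mismatch a separate and smaller matter. It is still an inconsistency.

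Three stronger readings are tempting, and the documents do not support them:

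- *No unforeseen event could ever be a USADE.* Step 3 of the working shows several routes that remain open.
- *A result of zero ADEs would be built in.* The anticipated effects in 3.1, such as skin allergy and superficial burns, have known patterns and can be rated related. The statement in 1.3.1 that no adverse device effects have been seen concerns earlier data, and nothing links it to this scale.
- *Every Unknown should be counted as related.* That would label as ADEs events whose relationship could not be determined. It is a debatable preference, and is not needed once the pattern condition is widened.

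**Conclusion.** The point holds as a defect of classification. Read literally, 4.2.2 sends a serious effect new in nature to Unknown when it matches no known device or procedure pattern and does not arise through the direct ADE routes. It then goes without the ADE, SADE and USADE labels. This conflicts with the purpose of 4.1.4 and with the step foreseen in 4.3.2. The scale in 4.3.1 is also inconsistent with 4.2.2, lacking two of its five levels.

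The size is modest. The documents give no basis for estimating how many events would be affected, and ADE counts are not among the endpoints listed in 2.2 or 5.1. The conclusion rests on two assumptions: that relatedness in the ADE definition is decided by the 4.2.2 scale, and that sites apply the wording of that scale as written. If investigators used broader judgement, fewer events would be mislabelled, but the rule would be applied unevenly.

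**What to change.** In 4.2.2, replace *known response pattern* with *known or plausible response pattern* in Possibly Related, Probably related and Related. Use the same five levels in 4.3.1 and in the CRF relationship field. Unknown then keeps its proper use, for events where the information does not allow a judgement.

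The cost is wording in two sections and the matching CRF options. No design feature, sample size or endpoint changes. The downside is that some additional events may be classed as device-related; the documents do not allow the number to be estimated.

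### The causality categories in 4.2.2 rate device and procedure as one item while the ADE definition concerns only KODEX or the comparator, so a purely procedural complication could be counted as a device effect

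*Combined protocol and SAP*

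**What the plan says.** The lead-in to the categories in 4.2.2 concerns the device alone: "The relationship or association of the study device in causing or contributing to the AE/SAE will be characterized as one of the following". Of the five categories that follow, *Possibly Related*, *Probably related*, *Related* and *Unknown* all refer to device and procedure as one item. *Related* begins "An AE that follows a plausible temporal sequence from the use of the study device/procedure" and excludes events that are reasonably explained by the subject's clinical state or by "other modes of therapy administered to the subject". *Not Related* uses a third term and adds a second condition: "No relationship between the AE and the administration of study treatment and a known relationship to other etiologies".

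The other sections divide as follows:

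- 4.3.1 asks, for each adverse event, for the relationship to the study device on three levels: unrelated, possible, probable.
- 4.3.2 (the event report form for USADEs, SAEs and SADEs) and 6.4 (investigator duties) ask for the relationship to device and procedure jointly.
- 4.1.1 defines an ADE as "An adverse event related to the use of KODEX-EPD System or accessories or the comparator". SADE (4.1.3) and USADE (4.1.4) build on that definition.
- The separate AE definition, also numbered 4.1.1, is the one that names procedural events: "Additionally, this definition includes events related to the procedures involved".

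**The concern.** KODEX-EPD is an imaging and occlusion-assessment system used during a cryoballoon ablation, which has complications of its own. The safety question about the device is which events are due to KODEX and which to the ablation. A category that is met when either cause applies cannot answer it.

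Such events are to be expected in the data, because 4.3.1 states that "only AEs directly or indirectly related to the EP intervention and/or any cardiac arrhythmia will be collected". At stake are the ADE, SADE and USADE classifications and their tabulation. So is the step at the end of 4.3.2, where a new SAE thought to be device-related may lead the sponsor to contact the investigator and, if warranted, to alert all investigators using the device. A genuine KODEX effect would also be harder to see if it carried the same code as procedural events.

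**Working it through.** No arithmetic applies, so the check sets the definitions against two hypothetical events.

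**Event A: an access-site bleed with no KODEX involvement.**

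1. Lead-in of 4.2.2 (device only): no relationship.
2. *Related* in 4.2.2: the bleed follows the procedure in time and fits a known response to the procedure, so the first two conditions are met through the procedure half of the joined term. The third turns on whether the ablation is one of the other therapies. The category itself names the procedure as a cause being rated, so the natural reading is that it is not. The synopsis, however, describes the ablation as standard therapy, which leaves the opposite reading open.
3. *Not Related* in 4.2.2: if study treatment includes the ablation, the first condition fails. If it means KODEX only, the first condition is met, but a known other cause is still required. The examples given there are concomitant medication and clinical state, not the ablation. The bleed does not fit cleanly either way.
4. Per-event item in 4.3.1: by its label (device only), unrelated. But its *possible* and *probable* levels are described nowhere except 4.2.2, where the wording is joined.
5. Serious-event form (4.3.2) and investigator duties (6.4): related, through the procedure.
6. ADE definition: not an ADE.

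**Event B: a skin reaction to a KODEX body patch** (3.1 lists skin allergy to the patches as an anticipated event).

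1. Lead-in, joined categories, per-event item and form: related in each.
2. ADE definition: an ADE.

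**Result.** A and B differ under the ADE definition but can receive the same code under 4.2.2 and 4.3.2. Event A alone has two defensible codes, depending on whether the investigator follows the lead-in or the category text, so the two sites could code it differently.

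**The levels also differ.** 4.2.2 has five and 4.3.1 has three; the three omit *Related* and *Unknown*.

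**The missing link.** No section asks for a procedure rating of its own, and none says which rating decides ADE, SADE or USADE status.

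**The case against.** The strongest reply is that ADE status does not depend on 4.2.2 at all. The ADE definition applies directly to KODEX, its accessories or the comparator, and procedural events are named under AE and not under ADE. The item in 4.3.1 is device-only, the forms themselves are not in the documents, and an investigator may treat the ablation as another therapy and so avoid *Related*. All of this is correct, and it limits the point to what could happen. It does not remove the conflict: 4.2.2 is the only place that defines degrees of relatedness, and it does so with device and procedure joined.

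A reader might go further in four ways that the documents do not support:

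- *Procedural complications are derived as ADEs, so ADE counts must be wrong.* No section derives ADE status from the 4.2.2 category.
- *They would trigger extra serious-event handling.* USADEs, SAEs and SADEs all go to the sponsor within 24 hours, any SAE is reportable whatever its cause, and 4.2.2 says that relationship does not decide what is reported.
- *They would contradict 1.3.1.* That section speaks of clinical data to date, which later counts cannot contradict.
- *A number of false ADEs can be calculated.* With a maximum of 2 × 20 + 25 = 65 patients, a complication risk p per patient and a share m of these miscoded, the expected number is 65 × p × m. At assumed risks of 3%, 5% and 10%, letting m run from 0 to 1 gives 0 to 1.95, 0 to 3.25 and 0 to 6.5. Neither p nor m is in the documents, and taking the upper ends presumes that every complication is miscoded.

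**Conclusion.** The point holds as a conflict between definitions. The plan asks for a device rating, defines four of its five levels for device and procedure together, and repeats the joined rating on the serious-event form and in the investigator duties. A purely procedural complication can therefore be rated as related. It could then be counted as a device effect if that rating is used to identify ADEs, SADEs, USADEs or SAEs thought to be device-related. That *if* is an assumption, because the plan gives no mapping.

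The number of events affected cannot be given from the documents. The effect is confined to safety classification and tabulation: the listed endpoints (5.1) include no safety endpoint, the analysis is descriptive (5.4.1), and SAE reporting to the sponsor does not change. The change should still be made, because attribution is best recorded when the event occurs and the repair is cheap.

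**What to change.** In 4.2.2, 4.3.1, 4.3.2, 6.4 and on the forms, use one set of causality levels and record three separate ratings for each event:

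- (a) the KODEX-EPD system and accessories, including use error and the injection made for its occlusion assessment;
- (b) the comparator, contrast venography;
- (c) the ablation procedure (cryoballoon and access).

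An event may be related under more than one rating. Replace the term study treatment in *Not Related* with the item being rated.

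State that ADE, SADE and USADE status follows ratings (a) and (b), as the ADE definition requires, and show KODEX-related and comparator-related events separately. Tabulate events related only to (c) on their own.

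Contrast should not be placed under the procedure. The comparator is venography with contrast, and in 2.6.2.1, step 4, the contrast injection is also part of the KODEX assessment. Grouping it with the ablation would remove events that the ADE definition includes.

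The cost is the added form fields and wording changes in four sections, with no extra patients or visits.
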